2.1.2.9 Scheduled study visit and window for the analysis

In order to summarize longitudinal data per time point, assessments will be allocated to visits using predefined time windows. Unless otherwise specified, when more than one assessment is available for a visit, all assessments will be listed under the visit while only the assessment closest to the planned day for the visit will be used for summaries and analyses.

Time windows are provided in Table 2-1.

Assessment	Visit	Time Window	Planned Visit Timing	Time Window Definition
Efficacy Assessm	nents		-	
Tumor response for imaging assessments	Screening	Baseline	Pre- treatment	D-42 to D-1 for whole body bone scans D-21 to D-1 for all other image scans
	C1D28	Between week 3 and week 4 ± 3 days	C1D28	D18 to D31
	C2D28 C4D28	C2D28 ± 7 days C4D28 ± 7 days	D56 D112	D49 to D63 D105 to D119
	every 8 v	,	ease progressio	n, i.e. C6D28, C8D28
	EOT	EOT + 14 days± 3 days		
Biomarkers				
Tumor Biopsy Sam	ples			
Fresh tumor biopsy	Screening	Baseline	Pre- treatment	D-14 to D-1
	C1D8 or	C1D8 ± 3 days or	D8 or	D5 to D11 or
	C1D16	C1D16 + 5 days± 3 days	D16	D13 to D24
	relapse			
CCI				

C = cycle, D = Day, 01 = start of study treatment

All other assessments (i.e. laboratory evaluations etc.) the reported visit will be used

Assessment	Visit	Time Window	PK assessment time point	Time Window Definition
Phase lb (Dose	C1D1	-03:00	< 00:00 pre-dose	C1D1, [-03:00, 00:00]
escalation)	C1D1	± 00:05	00:30 post-dose	C1D1, [00:25, 00:35]
	C1D1	± 00:15	01:30 post-dose	C1D1, [01:15, 01:45]
	C1D1	± 00:30	02:30 post-dose	C1D1, [02:00, 03:00]
	C1D1	± 00:30	04:00 post-dose	C1D1, [03:30, 04:30]
	C1D1	± 01:00	06:00 post-dose	C1D1, [05:00, 07:00]
	C1D1	± 01:00	08:00 post-dose	C1D1, [07:00, 09:00]
	C1D2	-03:00	< 00:00 pre-dose	C1D2, [-03:00, 00:00]
	C1D15	-03:00	< 00:00 pre-dose	C1D15, [-03:00, 00:00]
	C1D15	± 00:05	00:30 post-dose	C1D15, [0:25, 00:35]
	C1D15	± 00:15	01:30 post-dose	C1D15, [01:15, 01:45]
	C1D15	± 00:30	02:30 post-dose	C1D15, [02:00, 03:00]
	C1D15	± 00:30	04:00 post-dose	C1D15, [03:30, 04:30]
	C1D15	± 01:00	06:00 post-dose	C1D15, [05:00, 07:00]
	C1D15	± 01:00	08:00 post-dose	C1D15, [07:00, 09:00]
	C1D16	-03:00	< 00:00 pre-dose	C1D16, [-03:00, 00:00]
	C2D1	-03:00	< 00:00 pre-dose	C2D1, [-03:00, 0:00]
	every c	ycle Day 1 (pre	e-dose), up to Cycle 10 C10D1), i.e. C3D1, C4D1,,
Phase II arm 2 +	C1D1	-03:00	< 00:00 pre-dose	C1D1, [-3:00, 000:00]
Phase II arm 3	C1D1	± 00:05	00:30 post-dose	C1D1, [0:25, 000:35]
(Phase II arm 1, if required)*** /	C1D1	± 00:15	01:30 post-dose	C1D1, [01:15, 01:45]
Phase II arm A	C1D1	± 00:30	02:30 post-dose	C1D1, [02:00, 03:00]
	C1D1	± 01:00	05:00 post-dose	C1D1, [04:00, 06:00]
	C1D1	± 01:00	08:00 post-dose	C1D1, [07:00, 09:00]
	C1D2	-03:00	< 00:00 pre-dose	C1D2, [-03:00, 00:00]
	C1D15	-03:00	< 00:00 pre-dose	C1D15, [-03:00, 00:00]
	C1D15	± 00:05	00:30 post-dose	C1D15, [00:25, 00:35]
	C1D15	± 00:15	01:30 post-dose	C1D15, [01:15, 01:45]
	C1D15	± 00:30	02:30 post-dose	C1D15, [02:00, 03:00]
	C1D15	± 01:00	05:00 post-dose	C1D15, [04:00, 06:00]
	C1D15	± 01:00	08:00 post-dose	C1D15, [07:00, 09:00]
	C1D16	- 03:00	< 00:00 pre-dose	C1D16, [-03:00, 00:00]
	C2D1	-03:00	< 00:00 pre-dose	C2D1, [-03:00, 0:00]
every cycle Day 1 (pre-dose), up to Cycle 10, i.e. C3D1, C4D1, . C10D1), i.e. C3D1, C4D1, …,	

Notes:

C = *cycle*, *D* = *Day*, *hh:mm* = *hours and minutes*

00:00 = time of study treatment intake

Assessment	Visit	Time Window	PK assessment time point	Time Window Definition
*** first 10 patients in each	arm only.			

2.1.2.10 Imputation rule of partial or missing dates/data

Imputation rule of partial or missing dates

The following rule will be applied to handle partial dates. When the day is missing, it is imputed to the 15th of the month (e.g., DEC2007 imputed to 15DEC2007). When the day and month are both missing then the date is imputed to July 1st of that year (e.g., 2007 imputed to 01JUL2007). All imputed data are flagged in the listings. Rules for imputing dates for adverse events (AEs), concomitant medications, and anti-neoplastic therapies are described separately in this section.

For computation of time intervals (e.g. elapse time between initial diagnosis to first recurrence/relapse), time interval should be set to missing when the imputation rule leads to a negative value.

As of the date of data cutoff for the purposes of reporting, continuing events (e.g. adverse events, concomitant medication, etc.) will be summarized using the cut-off date as the date of completion, with an indication within listings that the event is continuing.

For patients who discontinue the study with ongoing events, the discontinuation date will be used as the completion date of the event with the appropriate censoring.

Handling of missing data

Unless otherwise specified missing data will not be imputed. Handling of missing data will depend on the nature of the data:

- Baseline characteristics: number of patient with missing data will be reported and descriptive statistics will be computed on patients with non-missing data.
- RECIST best overall response (BOR): patients with missing or unknown BOR will be considered as failure in the overall response rate computation (see Section 3.5.1.1)
- Time-to-event endpoints: appropriate statistical methods will be used to account for censored patients (see Section 3.5.1.2)
- PK and biomarker data, laboratory data, ECG data, vital signs: number of patient with missing data will be reported and descriptive statistics will be computed on patients with non-missing data.

Missing data will simply be noted as missing on appropriate tables/listings.

AE data imputation

Missing and partial date for AE will be handled according to rules specified below.

There will be no attempt to impute the following:

• Completely Missing AE start dates

• AE start dates missing the year.

For partial AE start date, the date imputation will be based on the temporal relation between the partial date and start of treatment date.

For partial AE end date or completely missing end date (AE is ongoing), the date imputation will be based on the temporal relation between the partial date, the last contact date and the 30-day follow date. If the minimum date of the last contact date and 30-day FU date is before the AE start date (imputed or not), the imputed AE end date will be set to the AE start date.

Table 4-11 provides examples of the different considered imputations for AE start date.

Table 4-12 provides examples of the different considered imputations for AE end date.

AE start date imputation example scenarios

Partial AE start date	Treatment start date	Temporal relationship compared to treatment start	Imputed Date	
12mmyyyy	20OCT2001	Uncertain	<blank></blank>	
ddmmm2000	20OCT2001	Before	01JUL2000	
ddmmm2002	20OCT2001	After	01JAN2002	
ddmmm2001	20OCT2001	Uncertain	210CT2001	
ddSEP2001	20OCT2001	Before	15SEP2001	
ddOCT2001	20OCT2001	Uncertain	210CT2001	
ddNOV2001	20OCT2001	After	01NOV2001	
Table 2-4 AE end date imputation example scenarios				
Partial AE end date	Minimum (Last contact date, 30- day FU date)	Ongoing	Imputed Date	

Concomitant medication date imputation

200CT2001

200CT2001

200CT2001

200CT2001

200CT2001

200CT2001

20OCT2001

20OCT2001

Version 2.2

Missing

ddmmm2000

ddmmm2002

ddmmm2001

ddmmm2001

ddSEP2001

ddOCT2001

ddOCT2001

Table 2-3

Yes

No

No

No

Yes

No

No

Yes

200CT2001

31DEC2000

31DEC2002

31DEC2001

200CT2001

30SEP2001

310CT2001

200CT2001

The imputation of the start date and end data of concomitant medication will follow the same conventions as for AE start date and end date.

Incomplete date for anti-neoplastic therapies

Prior therapies

Start date:

The same rule which is applied to the imputation of AE/concomitant medication start date.

End date:

Imputed date = min (treatment start date -1, last day of the month), if day is missing;

Imputed date = min (treatment start date -1, 31DEC), if month and day are missing.

Date of progression:

Imputed date = min (treatment start date -1, last day of the month), if day is missing;

Imputed date = min (treatment start date -1, 31DEC), if month and day are missing.

If the end date or the date of progression is not missing and the imputed start date is after the end date or after the date of progression, use the min(end date, date of progression) as the imputed start date.

Post therapies

Start date:

Imputed date = max (last date of study drug + 1, first day of the month), if day is missing;

Imputed date = max (last date of study drug + 1, 01JAN), if day and month are missing.

End date: No imputation.

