3.5.1.2 Computation of time to event endpoints

Overall survival

Overall survival (OS) is defined as the time from start of treatment to date of death due to any cause. If a patient is not known to have died, survival will be censored at the date of last contact.

As of protocol amendment 10, survival follow-up is no longer performed for patients who have discontinued study treatment in the Phase II part of the study.

Progression free survival

Progression-free survival (PFS) is defined as the time from the date of first study treatment intake to the date of the first documented disease progression or death due to any cause.

By default, if disease progression or death is documented after one single missing tumor evaluation, the actual event date of disease progression/death will be used for the PFS event date. If disease progression or death is documented after two or more missing tumor evaluations, the PFS time of these patients will be censored at the date of the last tumor evaluation with overall lesion response of CR, PR or SD. Patients who begin a new antineoplastic therapy prior to disease progression or death will be censored at the last adequate tumor evaluation prior to the start of the new antineoplastic therapy.

As of protocol amendment 10, post-treatment disease progression follow-up is no longer performed for patients who have discontinued study treatment in the Phase II part of the study.

Time to (overall) response

Time to (overall) response (TTR) will be based on "responders" only and is the time between the date of first treatment administration and the first documented response (CR or PR).

Duration of overall response

Duration of overall response (DOR) will be based on "responders" only and is the time between the date of first documented response (CR or PR) and the date of first documented progression or death due to underlying cancer. If progression or death due to underlying cancer has not occurred, then the patient is censored at the date of last adequate tumor assessment.

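### Partial death dates take the generic mid-month or 1 July imputation with no floor at treatment start or last date known alive, so an imputed death can precede a scan, a contact or the first dose

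*SAP*

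**What the plan says.** SAP section 2.1.2.10 opens with a general rule. "When the day is missing, it is imputed to the 15th of the month", and "When the day and month are both missing then the date is imputed to July 1st of that year". It then lists the exceptions: "Rules for imputing dates for adverse events (AEs), concomitant medications, and anti-neoplastic therapies are described separately in this section". Death dates are not among them.

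The next sentence deals with intervals that become negative: the "time interval should be set to missing when the imputation rule leads to a negative value". Its only example is the interval from diagnosis to first recurrence or relapse.

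Under missing data, the same section says "Time-to-event endpoints: appropriate statistical methods will be used to account for censored patients" and points to section 3.5.1.2. That section defines OS as "the time from start of treatment to date of death due to any cause" and adds "If a patient is not known to have died, survival will be censored at the date of last contact". It counts death from any cause as a PFS event. Neither it nor the Kaplan-Meier methods in section 3.5.3.1 says how to treat a partial death date.

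**The concern.** Because death has no rule of its own, it takes the general one, and that rule ignores everything else known about the patient. Two results can follow.

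First, a death can be dated before a visit at which the patient was alive. That is an impossible sequence in the data.

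Second, a death can be dated before the first dose. Read literally, the negative-interval sentence then blanks the survival time. The patient cannot be censored at last contact, because that applies only to patients not known to have died. Nor can the patient count as an event, because there is no time. A known death would have no place in the Kaplan-Meier estimate, although section 3.5 says the Full Analysis Set is used for all efficacy analyses.

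Such losses would not be random. They could arise only from deaths in roughly the first six months, so they would push early OS and PFS upwards. Section 3.5.3.1 plans landmark estimates from 3 months for both endpoints. The final report still includes OS tables (14.2.2.1b and 14.2.2.1d) and PFS tables (14.2.3.1b and 14.2.3.1d).

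**Working it through.** The plan gives no figure on this point, so there is none to reproduce. The check applies its date rules directly.

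**Inputs.** Imputed death D* is the 15th of the recorded month, or 1 July of the recorded year (section 2.1.2.10). The interval is D* − S, where S is treatment start (section 3.5.1.2). The SAP gives no day-count formula for OS or PFS, so D* − S + 1 is also tried; section 2.1.2.6 uses that convention for study day.

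**When the interval is negative**

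- *Day missing.* D* − S < 0 needs a start after the 15th and a death in the same calendar month. The longest survival affected is a start on the 16th and death on the 31st: 31 − 16 = 15 days. With +1, a start on the 16th gives 15 − 16 + 1 = 0, which is not negative. The start must then be the 17th or later, and the longest survival affected is 31 − 17 = 14 days.
- *Day and month missing.* D* − S < 0 needs a start after 1 July and a death in the same year. The longest survival affected is 2 July to 31 December, 182 days. With +1 it is 3 July to 31 December, 181 days.

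**Worked dates**

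| Start | Last scan | True death | Recorded as | Imputed | Result |
|---|---|---|---|---|---|
| 20 Mar 2013 | – | 30 Mar 2013 (10 days) | Mar 2013 | 15 Mar 2013 | interval −5 days |
| 1 Aug 2013 | – | 20 Dec 2013 (141 days) | 2013 | 1 Jul 2013 | interval −31 days |
| 10 Jan 2013 | 24 May 2013 | 30 May 2013 (140 days) | May 2013 | 15 May 2013 | death 9 days before the scan |

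**How often, given that the date is partial.** Assume start dates uniform over 2012–2014 and deaths uniform over the first H days. These are assumptions, not figures from the SAP.

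| Missing part | Deaths within H days | Negative interval (with +1) |
|---|---|---|
| Day | 14 | 26% (23%) |
| Day | 28 | 13% (11%) |
| Day and month | 28 | 46% (46%) |
| Day and month | 180 | 25% (25%) |

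Share of imputed deaths that precede the last scan, by time from that scan to death:

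| Missing part | 7 days | 14 days | 28 days | 56 days |
|---|---|---|---|---|
| Day | 28% | 5% | 0% | 0% |
| Day and month | 48% | 46% | 42% | 35% |

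**With a floor.** Let A be the last date known alive. A is never before S or before the last scan. If D* is the later of the generic date and A + 1, capped at the end of the recorded month or year, then D* ≥ A. The cap cannot break this, because A cannot lie beyond the recorded period of death. No OS or PFS interval is then negative, and no imputed death precedes a scan.

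**The case against.** **The set-to-missing sentence may never have been meant for OS or PFS.** Its example is a disease-history interval, section 3.2.6 refers back to it for such intervals, and time-to-event endpoints have their own bullet. A reader might infer that the plan intends to discard known deaths; nothing in it says so. What stands is that the sentence is worded for time intervals in general, its example is only an example, and the time-to-event bullet deals with censoring alone. The missing floor does not depend on this sentence.

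**Only very early deaths are at risk.** That is tempting but wrong for year-only dates, where the reach is about 182 days.

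**The effect can be sized on the colorectal arm.** The interim passage in section 1 implies 28 planned patients (14 / 0.50). One lost early death would then move 24/28 = 85.7% to 24/27 = 88.9%, or 3.2 points, against a Greenwood half-width of about 13 points: 1.96 × √(0.857 × 0.143 / 28) = 0.13. But section 2.3 says that this arm stopped before its planned number, so 28 is not its analysed size. The figures show the mechanism only.

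**Imputation shortens survival.** It does so only for some patients. The 15th and 1 July are midpoints, and they lengthen other times: a death on 2 May becomes 15 May.

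**The plan bounds other dates.** This is partly true. Prior-therapy end dates are bounded by treatment start, and post-study therapy start dates by the last study drug date. Adverse event end dates are not fully bounded: some examples for events not ongoing run past the earlier of last contact and the 30-day follow-up date.

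**The circumstances are narrow and the stakes low.** This is right for day-missing dates, which need a start after mid-month and death within about two weeks in the same month. Imaging is 8-weekly after cycle 2, so a scan shortly before death will be uncommon. OS, PFS and duration of response are secondary endpoints with no hypothesis tests, and the primary endpoints do not use death-date intervals.

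**Conclusion.** The point holds as a minor defect in a stated rule. Followed as written, section 2.1.2.10 can place a death before the patient's last scan or contact, or before the first dose. In the last case the literal wording removes a known death from OS, and from PFS where death is the first event and is not already censored for missed assessments or new therapy.

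The reach is deaths within 15 days of a start after mid-month when the day is missing (14 with +1), and same-year deaths up to 182 days after a start later than 1 July when only the year is known (181 with +1). The direction of any loss is known: early OS and PFS estimates rise. Its overall size is not, because the SAP does not say how many death dates are partial, and the number may be small or zero. The percentages above are conditional on a partial date and rest on uniform start and death times.

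**What to change.** Add to section 2.1.2.10:

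*A partial death date is imputed as the later of (a) the generic date (15th of the month, or 1 July if the month is also missing) and (b) the last date known alive + 1 day, but not later than the last day of the recorded month (or of the recorded year if only the year is known). The rule setting negative intervals to missing does not apply to OS, PFS or DOR.*

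The upper limit is needed. Without it, a patient seen on 31 May whose death is recorded only as May would be dated 1 June, outside the recorded month.

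The cost is two sentences in the SAP and a short derivation step. OS censoring already requires a last contact date, and the last date known alive can be built from it. No new data are needed.

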Table 14.3.6.2.3d	ECG shift table based on notable values by treatment group/arm	Safety Set	Phase Ib/II, Triple Combination
Table 14.3.7.1d	Left ventricular ejection fraction worst CTC grade by treatment group/arm	Safety Set	Phase Ib/II, Triple Combination
Table 14.3.8.1d	WHO/ECOG performance status by treatment group/arm	Safety Set	Phase Ib/II, Triple Combination
Table 14.4.1.1a	Duration of exposure to study drug by treatment group	Safety Set	Phase lb, Dual Combination
Table 14.4.1.1b	Duration of exposure to study drug by arm	Safety Set	Phase II, Dual Combination
Table 14.4.1.1d	Duration of exposure to study drug by treatment group/arm	Safety Set	Phase Ib/II, Triple Combination
Table 14.4.1.2d	Dose reductions of study treatment by treatment group/arm	Safety Set	Phase Ib/II, Triple Combination
Table 14.4.1.3d	Dose delays of study treatment by treatment group/arm	Safety Set	Phase Ib/II, Triple Combination
Table 14.4.1.4a	Summary statistics of exposure of study treatment by treatment group	Safety Set	Phase Ib, Dual Combination
Table 14.4.1.4b	Summary statistics of exposure of study treatment by arm	Safety Set	Phase II, Dual Combination
Table 14.4.1.4c	Summary statistics of exposure of study treatment by treatment group/arm	Safety Set	Phase Ib/II, Dual Combination
Table 14.4.1.4d	Summary statistics of exposure of study treatment by treatment group/arm	Safety Set	Phase Ib/II, Triple Combination
Table 14.4.2.1d	Concomitant medications and significant non-drug therapies started prior to the start of study drug by	Safety Set	Phase Ib/II, Triple Combination

	preferred term and treatment group/arm		
Table 14.4.2.2d	Concomitant medications and significant non-drug therapies started after the start of study drug by preferred term and treatment group/arm	Safety Set	Phase Ib/II, Triple Combination
Table 14.4.2.3a	Antineoplastic therapy since discontinuation of study drug by preferred term and treatment group	Safety Set	Phase lb, Dual Combination
Table 14.4.2.3b	Antineoplastic therapy since discontinuation of study drug by preferred term and arm	Safety Set	Phase II, Dual Combination
Table 14.4.2.3d	Antineoplastic therapy since discontinuation of study drug by preferred term and treatment group/arm	Safety Set	Phase Ib/II, Triple Combination
Table 14.4.4.1.1	Summary of encorafenib concentrations by treatment group	Full Analysis Set	Phase Ib
Table 14.4.4.1.2	Summary of encorafenib concentrations by arm	Full Analysis Set	Phase II

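### Partial AE and concomitant-medication start dates of uncertain timing are imputed to the day after treatment start without checking the recorded end date, so some records start after they ended and are classed as on-treatment

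*SAP*

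**What the plan says.** Section 2.1.2.10 gives the AE start rule in one sentence: "For partial AE start date, the date imputation will be based on the temporal relation between the partial date and start of treatment date". The example table uses a treatment start of 20 October 2001 and labels two cases Uncertain:

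- month known, day missing: "ddOCT2001 20OCT2001 Uncertain 210CT2001"
- year known only: "ddmmm2001 20OCT2001 Uncertain 210CT2001"

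Both receive 21 October 2001, the day after treatment start.

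One sentence links AE start and end dates. If the earlier of last contact and 30-day follow-up "is before the AE start date (imputed or not), the imputed AE end date will be set to the AE start date". It moves an imputed end date, never a start date.

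For medications: "The imputation of the start date and end data of concomitant medication will follow the same conventions as for AE start date and end date".

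Prior anti-neoplastic therapy uses the same start rule with a correction. If the imputed start falls after a non-missing end or progression date, the SAP says to "use the min(end date, date of progression) as the imputed start date". That correction appears only under the anti-neoplastic heading.

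Three other places use the resulting dates:

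- Section 2.1.2.8 opens the on-treatment window at first administration of study treatment.
- Section 3.3.2 summarises medications that start on or after treatment start, or that start earlier and continue. Those that start and end earlier are only listed.
- Section 4.1.1 plans Table 14.1.4.5d for medications stopped before study drug, and Table 14.4.2.2d for concomitant medications and "significant non-drug therapies started after the start of study drug by" preferred term.

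**The concern.** Placing an uncertain start just after the first dose is a common cautious convention, and it is not the problem here. The problem is that it is applied even when the recorded end date has already settled the question. An event that ended on 10 October cannot have begun on 21 October, yet the written rule says that it did.

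Two kinds of output depend on this date. For AEs, onset decides whether the event falls in the on-treatment window and so, on the natural reading, in the treatment-emergent tables. For medications, the start date decides between the concomitant summary and the prior listing. A programmer who follows the text literally produces impossible date pairs. One who corrects them silently departs from the plan.

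**Working it through.** **Inputs, all from section 2.1.2.10 unless stated.** Treatment start T = 20 October 2001. Uncertain start: imputed start S = T + 1 = 21 October 2001. On-treatment if S ≥ T (section 2.1.2.8, applied to onset; the upper end of the window does not matter here).

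**Step 1: reproduce the SAP's table.** The rows imply four rules: year missing gives blank; an earlier period gives the 15th of the month or 1 July; a later period gives the 1st of the month or 1 January; an uncertain period gives T + 1. Applied to the seven start-date rows, these return all seven imputed dates.

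**Step 2: add a recorded end date E.** The cap is S* = min(S, E).

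| Partial start | Recorded end E | SAP start S | E − S (days) | On-treatment under SAP | Capped start S* | On-treatment with cap |
|---|---|---|---|---|---|---|
| ddOCT2001 | 10 Oct 2001 | 21 Oct 2001 | −11 | yes | 10 Oct 2001 | no |
| ddOCT2001 | 19 Oct 2001 | 21 Oct 2001 | −2 | yes | 19 Oct 2001 | no |
| ddmmm2001 | 10 Mar 2001 | 21 Oct 2001 | −225 | yes | 10 Mar 2001 | no |
| ddmmm2001 | 30 Sep 2001 | 21 Oct 2001 | −21 | yes | 30 Sep 2001 | no |
| ddOCT2001 | 25 Oct 2001 | 21 Oct 2001 | +4 | yes | 21 Oct 2001 | yes |

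The fourth row also covers a partial end. An end of ddSEP2001 is imputed to 30 September 2001 by the SAP's end-date table, still 21 days before the imputed start. The last row shows that the cap leaves the cautious convention alone when the end date does not contradict it.

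**Step 3: scan all pre-treatment end dates in the example.**

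- Month-only start, ends 1 to 19 October: 19 of 19 on-treatment under the SAP; 0 of 19 with the cap.
- Year-only start, ends 1 January to 19 October: 292 of 292 under the SAP; 0 of 292 with the cap.

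**Step 4: look for a repair elsewhere in the text.**

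- The AE start/end rule changes an imputed end date and is triggered by last contact or 30-day follow-up. A complete recorded end is not imputed, so the rule does not reach it.
- The negative-interval rule blanks a computed interval (for example, the −11 days above). It changes neither the date nor the classification.
- The cap for prior anti-neoplastic therapy is confined to that heading.

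**Step 5: follow one medication through the outputs.** Start ddOCT2001, end 10 October 2001, imputed start 21 October 2001. Under section 3.3.2 it starts after treatment start, so it is summarised as concomitant and fits Table 14.4.2.2d. By its stop date it also fits Table 14.1.4.5d. The two tables give contradictory accounts of one record.

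**The case against.** Several points on the other side are sound.

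- **The affected class is narrow.** It needs a partial start in the month of treatment start, or a year-only start in its year, together with an end before treatment. Starts in an earlier month or year are imputed before treatment, and complete starts are not imputed. This stands.
- **The AE consequence is partly inferred.** The SAP uses treatment-emergent in table titles without defining it, and when AE recording begins is left to the protocol. If few pre-treatment events are recorded as AEs, few are affected. This stands; the medication consequence does not depend on it, because section 3.3.2 is explicit.
- **The anti-neoplastic cap had its own reason.** Imputed end and progression dates of prior therapies are held to the day before treatment at the latest, so a start of T + 1 would contradict them automatically. That explains why the cap was written there. It does not make the result right for an AE or medication with a recorded pre-treatment end.
- **A cap at any imputed end would collide with existing text.** Suppose an AE is ongoing, its start is ddOCT2001, and treatment start and last contact are both 20 October. The present rule moves the end to 21 October; an unrestricted cap would move the start to 20 October. This stands and limits the fix.
- **The error is visible and over-counts safety events.** Imputed data are flagged in listings, which helps for AEs (Listing 16.2.7.1). Section 4.1.2 plans no concomitant-medication listing for the final report, and a flag does not correct a table count.

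**Conclusion.** The point holds as a gap in a stated rule. For uncertain partial starts whose recorded end precedes treatment, section 2.1.2.10 gives a start after the record's own end, and nothing else in the SAP corrects it. Within that class the result is always wrong. The size of the class is unknown and may be small. The AE part assumes that section 2.1.2.8 is applied to onset date.

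Three stronger readings are tempting but unsupported:

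- A reader might take the share of calendar days before 20 October (19/31 = 61% of the month, 292/365 = 80% of the year) as a misclassification rate. Those shares describe possible true start dates under the T + 1 convention, assuming uniform onset. That convention is kept here, and the cap acts only where an end date contradicts it.
- A reader might infer that every record ending before treatment is misclassified. The SAP's own rows refute this: ddSEP2001 becomes 15 September 2001 and ddmmm2000 becomes 1 July 2000, both before treatment.
- A reader might expect long-standing medications to be hit hardest. The SAP gives no evidence for this. A medication begun in an earlier year is placed in that year, and one that continues into treatment has no pre-treatment end date.

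**What to change.** Add one rule to section 2.1.2.10, under both the AE and the concomitant-medication headings: *If the recorded AE or concomitant-medication end date (complete, or partial with its imputed last possible date) is before the imputed start date, set the imputed start date to that end date.*

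State its limits alongside it:

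- The cap does not apply to end dates imputed from last contact or 30-day follow-up for ongoing or missing ends. The existing end-date rule stays in force for those.
- Where the end is partial and both rules could act, apply the cap first, so that a recorded pre-treatment end is not moved to the imputed start.
- Uncertain starts without such an end date stay at treatment start + 1.

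Adding an example row with an end date before treatment would make the rule unambiguous for programmers. The cost is a few sentences and a small change to the date derivation, reusing logic already specified for prior anti-neoplastic therapy. No new data are needed.
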